**Night-time voiding log:**

The subject/parents will be instructed to record a night-time voiding log specifying the number of incontinent episodes per night. This log is included in the IRB application. Subjects/parents will fill out the log for a two week period prior to foot stimulation to determine a baseline average of nocturnal enuresis episodes, during the two week foot stimulation period to measure any acute effect on nocturnal enuresis episodes and finally during the two weeks after stimulation to evaluate any post-stimulation residual benefit.

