**Neuromodulation:**

In the office to calibrate TENS device - skin surface electrodes will be attached to the bottom of one foot for electrical stimulation. The stimulator and electrodes are FDA-approved devices for TRANSCUTANEOUS ELECTRICAL NERVE STIMULATION (TENS) and are commercially available. The stimulation characteristics include a continuous frequency of 5 Hz, pulsewidth 0.2 ms, and intensity 2-4 times the threshold voltage required for inducing

toe twitching - or the intensity that the subject feels comfortable with. The subjects will also be instructed how to use the stimulator and where to attach the electrodes on the foot at the beginning of the study. The investigator will provide the stimulator and electrodes. The subjects will be asked to wear socks to prevent the electrodes from detachment and to stop the stimulation during walking or in any non-resting situation. Subjects will be provided a TENS device and disposable foot pads for two weeks of treatment. Subjects will be asked to use the stimulator for a MINIMUM of 60 minutes in the evening prior to bedtime at home for two weeks. They will be encouraged to use the stimulator for more time than the minimum as long as they accurately record the total duration. Stimulation will be performed during the second and third weeks of the study only.

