#### Questionnaire:

Subjects will complete the quality of life questionnaire attached to this application at the start of the study (prior to week 1) to establish a baseline, after the second week of treatment period (week 4 of study) to determine a treatment effect, and after the sixth week to determine any residual post-treatment effect.

The subjects can call or email the investigators anytime during the 6-week at-home test for questions or any problems encountered. At the end of the 6-week study, the subjects are asked to return the stimulator and night-time voiding log to the investigator's office.

Subjects who feel they are having a positive response to TENS treatment and would like to continue participation in the study for an additional 6 weeks may do so. We will ask that they continue to keep their logs and answer the questionnaires

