**2.17 What are the main outcome variables that will be evaluated in this study?**

1) Number of night-time incontinent episodes per two week period comparing baseline number of voids (first two weeks of study), number during two-week stimulation period (weeks 3-4), and number during two-week after-stimulation period (weeks 5-6).

2) Subjective quality of life measures as recorded by validated quality of life questionnaire prior to study start, after week 4 and after week 6 to evaluate for any differences.

3) For the subjects who continue participation for an additional 6 weeks, we hope to prove long-term efficacy and sustainability in symptom relief, and to ensure no unanticipated adverse outcomes with continued usage

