**Indicate why direct consent is not possible:**

Study participants will all be children < age 18 years old and therefore consent will be obtained from a parent or legal guardian.

[\[reviewer notes-\]](#)

**4.11 At what point will you obtain the informed consent of potential research subjects or their authorized representative?**

After performing certain of the screening procedures, but prior to performing any of the research interventions/interactions

**4.11.1 Address why you feel that it is acceptable to defer obtaining written informed consent until after the screening procedures have been performed.**

Our screening procedure only includes a review of patient medical record. We have a requested a waiver of consent for assessing medical record and provided the reasons for the waiver on section 4.7

**4.11.2 Taking into account the nature of the study and subject population, indicate how the research team will ensure that subjects have sufficient time to decide whether to participate in this study. In addition, describe the steps that will be taken to minimize the possibility of coercion or undue influence.**

The research study will be discussed in detail with the child's parent or guardian in the outpatient clinic by the pediatric urologist. If the parent is immediately interested in enrolling the child in the study, informed consent will take place during the clinic visit as will the providing of the TENS equipment will all necessary teaching on the use of the device. If the parent would like additional time to consider participation, we will wait for them to contact us at a later date. The intention for participation will always be initiated by the parent, thus we will make no attempts to call or email them if they do not contact us after the clinic visit.

[\[reviewer notes-\]](#)

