**5.3 All the risk questions (screening, intervention/interaction, follow-up) have been merged into one question (5.1).**

[\[reviewer notes-\]](#)

**5.4 Do any of the research procedures pose a physical or clinically significant psychological risk to women who are or may be pregnant or to a fetus?**

\* No

[\[reviewer notes-\]](#)

**5.5 Do any of the research procedures pose a potential risk of causing genetic mutations that could lead to birth defects?**

\* No

[\[reviewer notes→\]](#)

**5.6 Are there any alternative procedures or courses of treatment which may be of benefit to the subject if they choose not to participate in this study?**

\* Not applicable

If **Yes**, describe in detail:

[\[reviewer notes→\]](#)

**5.7 Describe the specific endpoints (e.g., adverse reactions/events, failure to demonstrate effectiveness, disease progression) or other circumstances (e.g., subject's failure to follow study procedures) that will result in discontinuing a subject's participation?**

\* Describe below:

The study is expected to end when the six weeks have been completed with associated completion of weekly night-time voiding log and quality of life questionnaires. However, if the subject can not follow the study procedures such as an inability to tolerate foot stimulation or non-compliance with completing night-time voiding logs and/or quality of life questionnaires, the subject's participation will be discontinued and the study will be ended.

We expect some electrodes to detach from the foot. However, occasional unattached electrodes will not end the study, since the data will be collected in a week period and a few occurrences of detachment should not change the results. Also, if skin irritation is caused by the electrodes, the study will continue by using the other foot and giving the irritated foot a day or two to recover. However, if unexpected serious irritation occurs that cannot be avoided by changing feet, the study will be terminated for that subject.

[\[reviewer notes→\]](#)

**5.8 Will any individuals other than the investigators/research staff involved in the conduct of this research study and authorized representatives of the University Research Conduct and Compliance Office (RCCO) be permitted access to research data/documents (including medical record information) associated with the conduct of this research study?**

\* No

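### The log for all three windows comes back once, at week 6, with no described staff check before then, so the baseline stays open to revision after open-label treatment

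*Combined protocol and SAP*

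**What the plan says.** Section 2.17 defines outcome 1 as "Number of night-time incontinent episodes per two week period comparing baseline number of voids (first two weeks of study", set against the count in weeks 3-4 (stimulation) and weeks 5-6 (after stimulation). Section 2.3 describes an open-label comparison within each child, and 2.3.1 confirms that there is no placebo arm.

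The source is a family-kept record. Under Night-time voiding log in 2.6, "Subjects/parents will fill out the log for a two week period prior to foot stimulation to determine a baseline average of nocturnal enuresis episodes".

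On the device, 4.11.2 says that if the parent is interested straight away, "informed consent will take place during the clinic visit as will the providing of the TENS equipment", with teaching. The Neuromodulation text in 2.6 also has families taught how to use the stimulator and "where to attach the electrodes on the foot at the beginning of the study".

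On return, the Questionnaire text in 2.6 says: "At the end of the 6-week study, the subjects are asked to return the stimulator and night-time voiding log to the investigator's office". No earlier return of the log is described.

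On contact, the same text lets families call or email at any time. Section 2.7 answers No to follow-up procedures for research, a question that names phone calls. The one scheduled call, in 5.13, falls in the optional extension and concerns problems and tolerability.

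Section 5.7 provides that for "non-compliance with completing night-time voiding logs and/or quality of life questionnaires, the subject's participation will be discontinued". It gives no threshold and no date on which completion is reviewed.

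**The concern.** There is no control arm, so nothing offsets an error in the baseline count. The family holds the baseline page until two weeks after treatment ends and knows which weeks were treated. Entries filled in or adjusted late could recall the baseline as worse than it was, which would look like improvement. Stimulation during baseline nights would act the other way, lowering the baseline and hiding an effect. Neither would come to staff attention before week 6 unless the family raised it.

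Two practical losses follow. A child whose baseline was never recorded drops out of the main comparison, because at week 6 those nights can no longer be observed. And 5.7 relies on seeing that logs are incomplete, while the plan describes no moment in weeks 1-6 at which staff look.

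**Working it through.** The plan states no figure to reproduce: 3.12 calls the variability unknown and chooses 25 subjects without a calculation. The check is therefore a timeline, followed by illustrations on assumed values.

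**Timeline**

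| Time | Event | Source | Staff see the log? |
|---|---|---|---|
| Enrolment visit | Consent, teaching, device handed over (families who enrol at once) | 4.11.2; 2.6 Neuromodulation | Not started |
| Weeks 1-2 | Baseline log at home | 2.6 Night-time voiding log; 2.17 | None described |
| Weeks 3-4 | Stimulation at home, log continues | 2.17; Aim #2 in 1.2 | None described |
| After week 4 | Questionnaire | 2.6 Questionnaire | Return of the log not mentioned |
| Weeks 5-6 | Post-stimulation log | 2.17 | None described |
| End of week 6 | Log and device returned | 2.6 Questionnaire | First described sight |

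The log covers 3 x 14 = 42 nights per child, in up to 25 children. The review after 10 subjects in 5.13 works on data already collected, so it is not an interim check on an individual child.

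The schedule is itself inconsistent. The Neuromodulation text places stimulation in the second and third weeks, while 2.17 and Aim #2 place it in weeks 3-4. On the first reading, week 2 is both a baseline week and a stimulation week, so the end of the baseline window is not uniquely defined.

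**Illustration 1: sensitivity of a small baseline.** Section 3.13 admits children with 4 episodes per month. Taking a month as 30 days, the expected 14-night count is 4 x 14/30 = 1.87, so one misrecorded night is 1/1.87 = 54% of baseline. At 15 per month the baseline is 7.0 and one night is 14%.

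**Illustration 2: baseline recalled as worse (assumed values).** A child truly at 7 episodes in each window, with baseline recalled as 9, shows a fall of (9 - 7)/9 = 22% with no effect. That is one child. If 5 of 25 families did this, the mean change shifts by 5 x 2/25 = 0.4 episodes. The group baseline becomes 7.4, an apparent fall of 0.4/7.4 = 5.4%.

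**Illustration 3: effect on a test.** Section 2.18 names the t-test and ANOVA without alpha or sidedness. I assume a two-sided 0.05 paired t-test, n = 25, no true effect, and noncentrality = shift x sqrt(25)/SD of differences. The rejection rates are:

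| Mean baseline shift (episodes) | SD 1.5 | SD 2 | SD 3 |
|---|---|---|---|
| 0.4 | 25% | 16% | 10% |
| 1.0 | 89% | 67% | 36% |

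**Illustration 4: the opposite direction.** With a true relative reduction r on stimulated nights, no carry-over, and the device used on 7 of 14 baseline nights, the apparent reduction is 1 - (14 - 14r)/(14 - 7r). For r = 0.5 this is 1 - 7/10.5 = 33%. For r = 0.3 it is 1 - 9.8/11.9 = 18%. A real effect is understated.

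**The case against.** The strongest case on the other side is that silence in the visible text is weak evidence. The log form is an upload that is not reproduced, so it may carry dated or timed entries. The abstract calls for a daily log, so completion from memory would be a deviation and not the plan. Families are asked to record the total duration of stimulation, which is a record of device use, though self-reported. Section 5.7 speaks of a weekly log and of data gathered over a week. In a 25-child uncontrolled pilot, how often diaries are collected may seem a matter of preference.

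Much of this limits the wording. A reader might infer that the baseline cannot be verified at all; the documents support only that no check is described. A reader might infer that the 5.7 provision cannot be applied. But gaps are visible at week 6, a family can report them sooner, children entering the extension are still in the study at that point, and the return date of the questionnaires is not stated. A reader might take it as stated that the device is at home during baseline. That is a reasonable inference from 4.11.2 read with the log schedule, and 4.11.2 covers families who enrol at once.

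The rest does not remove the point. Dates written by the family do not show when entries were made. The weekly wording in 5.7 sets no weekly return. Recorded durations appear to reach staff no earlier than the log does.

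**Conclusion.** The concern holds in this form: no staff sight of the log is described between enrolment and the end of week 6, so the baseline for outcome 1 remains open to unseen completion or correction after open-label treatment, a missing baseline is found too late to recover, and 5.7 has no described review point for log completion in weeks 1-6.

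It would be tempting to conclude that the results will be biased in favour of treatment. The documents do not support that. Late recall and early device use pull in opposite directions, nothing shows that either will occur, and no SD or effect size is given. The 22%, the 0.4 episodes and the rejection rates all rest on assumed values. They show that modest recording errors could matter at this sample size, not that they will arise. The point is worth acting on because the baseline carries the whole comparison and the remedy is cheap.

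**What to change.** In 2.6, ask families to send a photograph or copy of the ID-coded log, including the recorded stimulation durations, at the end of the baseline window and again at the end of the stimulation window, with the original returned at week 6 as now. Treat the copy received as the record for that window and log any later change as a dated correction. State when log completeness for 5.7 is reviewed.

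Reconcile the second-and-third-week wording under Neuromodulation with weeks 3-4 in 2.17 and Aim #2, so that the end of the baseline window is defined. This recommendation adds no rule on when stimulation starts or when a child is discontinued.

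The cost is two short messages per family, an acknowledgement by existing staff, secure handling of emailed logs (5.15 promises ID-only data forms, but an email shows its sender), and an update to the No in 2.7. No extra visit is needed. The copy does not prove nightly entry or that the device was unused during baseline. It does prevent unseen revision of the baseline after treatment.

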### 2.6.1 Will blood samples be obtained as part of this research study?

\* No

\*If submitting a protocol for expedited review, it should be clear that the planned blood draws are within the parameters described here: <http://www.hhs.gov/ohrp/policy/expedited98.html> (see Expedited Research Category #2)

If **Yes**, address the frequency, volume per withdrawal, the total volume per visit, and the qualifications of the individual performing the procedure:

**Study Flow Chart:**

Name	Modified Date
------	---------------

[\[reviewer notes~\]](#)

- 2.7 Will follow-up procedures be performed specifically for research purposes? Follow-up procedures may include phone calls, interviews, biomedical tests or other monitoring procedures.**

\* No

[\[reviewer notes~\]](#)

- 2.8 Does this research study involve the use of any questionnaires, interview or survey instruments?**

\* Yes

**Upload a copy of all materials except for the SCID or KSADS which are on file at the IRB. The use of all instruments must be addressed in question 2.6 and/or question 2.7 (except for an exempt submission where they should be addressed on the appropriate uploaded exempt form).**

Name	Modified Date
Quality of Life Survey	8/12/2014 8:56 PM
Night-time Voiding Log	8/12/2014 8:53 PM

**Previously the name and publisher for commercially available materials were listed in the textbox below but effective 9/1/2015, all materials (except for the SCID and KSADS) must be uploaded using the Add button above.**

[\[reviewer notes~\]](#)

- 2.9 If subjects are also patients, will any clinical procedures that are being used for their conventional medical care also be used for research purposes?**

\* yes

If **Yes**, describe the clinical procedures (and, if applicable, their frequency) that will be used for research purposes:

We will not perform a urinalysis specifically for this research project. However, the result of urinalysis as part of standard clinical care will be reviewed in the medical record and used to screen the patients for eligibility.

**2.10** The blood sample question was moved to 2.6.1.

[\[reviewer notes→\]](#)

**2.11** **What is the total duration of the subject's participation in this research study across all visits, including follow-up surveillance?**

\* 6 to 12 weeks

[\[reviewer notes→\]](#)

**2.12** **Does this research study involve any type of planned deception?**

If Yes, you are required to request an alteration of the informed consent process (question 4.7)

\* No

[\[reviewer notes→\]](#)

**2.13** **Does this research study involve the use of UPMC/Pitt protected health information that will be de-identified by an IRB approved "honest broker" system?**

\* No

[\[reviewer notes→\]](#)

**2.14** **Will protected health information from a UPMC/Pitt HIPAA covered entity be accessed for research purposes or will research data be placed in the UPMC/Pitt medical record?**

\* Yes

If you answer **Yes**, you are required to submit this study to the Center for Assistance in Research using e-Record (CARE). Per UPMC Policy HS-RS0005, all research projects that access or involve UPMC electronic protected health information (e-PHI) must be submitted to CARE, with the exception of clinical trials that are contracted through the UPMC Office of Sponsored Programs and Research Support (OSPARS).

Complete the online submission form at <https://care.upmc.com/request.aspx>. After the study is submitted in OSIRIS, a CARE representative will conduct a review. You will be notified once your

CARE review is complete or if anything further is needed.

Studies that will access only paper-based medical records (not in combination with any electronic records) do not need to be submitted to CARE.

For additional information, please see <https://care.upmc.com>.

**Describe the medical record information that will be collected from the UPMC/Pitt HIPAA covered entity and/or the research-derived information that will be placed in the medical records.**

Medical records will be accessed for screening the patients for eligibility and information concerning the child's diagnosis, age, past medical history, and diagnostic procedures that were already done as part of their standard medical evaluations will be retained for this study. A urinalysis is normally done as part of standard of care and will be checked in the medical record for evidence of urinary tract infection. The standard office visit questions, which is also available in the medical record and includes questions about prior neurological disorders, spinal cord injuries, and so forth, will be reviewed to rule out those who may have a neurological reason for nocturnal enuresis. No research data will be placed in the medical record.

**2.14.1 Will protected health information from a non-UPMC/Pitt HIPAA covered entity be obtained for research purposes or will research data be placed in the non-UPMC/Pitt medical record?**

\* No

I, [name], certify that any member of my research team accessing, reviewing and/or recording information from medical records have completed the CITI Privacy & Information Security course or, if completed within the past year, the Internet-Based Studies in Education and Research (ISER) HIPAA for Researchers (Formerly RPF Module 6). The HIPAA certificates must be available for review if audited but do not need to be uploaded into this OSIRIS application.

\* Yes

**2.14.2 Are you requesting a waiver of the requirement to obtain written HIPAA authorization for the collection of the PHI?**

\* No

[\[reviewer notes~\]](#)

**2.15 Does this research study involve the long-term storage (banking) of biological specimens?**

\* No

[\[reviewer notes~\]](#)

**2.16 Will research participants be asked to provide information about their family members or acquaintances?**

\* No

[\[reviewer notes~\]](#)

**2.17 What are the main outcome variables that will be evaluated in this study?**

1) Number of night-time incontinent episodes per two week period comparing baseline number of voids (first two weeks of study), number during two-week stimulation period (weeks 3-4), and number during two-week after-stimulation period (weeks 5-6).

2) Subjective quality of life measures as recorded by validated quality of life questionnaire prior to study start, after week 4 and after week 6 to evaluate for any differences.

3) For the subjects who continue participation for an additional 6 weeks, we hope to prove long-term efficacy and sustainability in symptom relief, and to ensure no unanticipated adverse outcomes with continued usage

**2.18 Describe the statistical approaches that will be used to analyze the study data.**

\* Addressed below:

The data will be statistically analyzed using student t-test and ANOVA

[\[reviewer notes~\]](#)

**2.19 Will this research be conducted in (a) a foreign country and/or (b) at a site (e.g., Navajo Nation) where the cultural background of the subject population differs substantially from that of Pittsburgh and its surrounding communities?**

\* No

Note that copies of training records, licenses, certificates should be maintained in the study regulatory binder and are subject to audit by the Research Conduct and Compliance Office (RCCO).

In addition, individuals planning to conduct human subject research outside the United States must complete an optional module on the CITI training website: International Studies. [Click here](#) to access the instruction sheet for accessing optional CITI modules.

[\[reviewer notes~\]](#)

